## DD-CA Protocol

The Dulce Digital-COVID Aware (DD-CA) study will enroll a total of 172 COVID + and – Hispanic patients with type 2 diabetes according to the inclusion and exclusion criteria outlined below. This study compares discharged patients requiring on-going glucose management who receive a proven texting platform with added COVID-related messages versus discharged patients requiring on-going glucose management who do not receive COVID educational messaging using a digital texting platform.

Inclusion criteria:

- Are a patient admitted to a Scripps Mercy Hospital
- Self-identify as Hispanic/Latino
- Are 18 years of age or older
- Speak English or Spanish
- Have type 2 diabetes diagnosis and A1c  $\geq$  7% in the last 30 days
- Have a cellphone that can receive/send text messages

Exclusion criteria:

- Are pregnant
- Are currently participating in another diabetes or COVID-19 related study
- Do not meet all eligibility inclusion criteria

Research staff review automated electronic health record (EHR) reports to identify potentially eligible patients. Once a patient is determined eligible according to EHR-based study criteria, the attending physician is contacted to approve inclusion in the study. If the nursing staff approved and indicate anticipated discharge to home in <24 hours, the patient is asked if he/she is willing to discuss the study with the research staff. Patients interested in the study are approached by a trained bilingual staff member while inpatient. Patients who are deemed eligible to participate in the study are provided with a copy of the consent form and review all content together with the staff member in Spanish or English (depending on potential participant's language preference). Adequate opportunity is provided to the potential participant to consider all options and ask questions; care is taken to ensure that all participants understand the information and that their participation is voluntary.

After consent is obtained and the patient is enrolled to the study, research staff verbally administer the baseline survey, then unveil the group assignment (enclosed in sealed envelopes by the statistician) to the patient: Intervention group (DD-CA + DTS) or Usual Care group (DTS). Each participant is assigned a unique ID number for de-identification purposes.

For all participants, a routine referral is placed to the Diabetes Transition Service (DTS) program, which is a standard service offered to patients with diabetes approaching discharge from Scripps Mercy Hospital. As part of DTS, participants receive pre-discharge diabetes education from a certified diabetes care and education specialist (CDCES). Within 10 days of discharge, participants are contacted by a DTS health coach using a standardized protocol to coordinate care with outpatient health and other community resources to collaborate with participants in overcoming barriers to accessing these resources. The DTS health coach also provides important training on glucose pattern and excursion recognition. For participants in the Intervention group, the glucose control review/feedback is informed by glucose data that is wirelessly transmitted via the study meter and populated in the study dashboard. In Usual Care

this review/feedback is based on participants' self-report of recent glucose values. Aside from this difference, standard DTS delivery is otherwise constant across intervention groups.

In addition to the DTS program described above, participants assigned to the Intervention group (DD-CA) receive an evidence-based text message-based diabetes self-management education and support in their language of preference (Spanish or English), which consists of educational, motivational and medication adherence messaging. The messaging is supplemented by COVID-related support content and is tailored to address identified barriers in Hispanic underserved communities (e.g., obtaining testing supplies and medications, accessing routine medical care, and completing other important diabetes self-management behaviors such as healthful eating, exercise, social distancing, quarantine, and stay-at-home/lockdown guidelines).

The EHR of all study participants will be audited for specific information relevant to the trial including hospital readmission rates within 30 (primary outcome), 90 and 180 days, length of stay for 30-day readmissions, healthcare costs, patient descriptives, and other relevant clinical metrics (e.g., HbA1c).

All participants are asked to complete three assessments of approximately 15-20 minutes duration at baseline/prior to hospital discharge, and at 90 days and 180 days by telephone.

Data collected during all assessments will include the following patient-reported indicators:

1. Demographic information (study-specific/standard item)
2. Diabetes distress, measured using the Diabetes Distress Scale
3. Diabetes self-management behaviors, measured using the Summary of Diabetes Self-Care Activities Survey
4. Patient-reported physical and mental health, measured using the Patient-Reported Outcomes Measurement Information System Global-10 Health Scale (PROMIS)
5. Knowledge and attitudes towards COVID-19 and COVID-19 diagnosis status, measured using the COVID-19 Patient Survey (Phenix toolkit).

The RE-AIM framework will be used to evaluate the success of the DD-CA versus Usual Care in 1) Reaching a representative segment of the population (Reach); 2) Achieving meaningful outcomes through a well-implemented intervention (Efficacy/Implementation); 3) Creating an intervention that can be adopted by and maintained in a real-world environment (Adoption/Maintenance). As part of the process evaluation, participants from both groups are invited to participate in a telephone-based survey to assess patient experiences and satisfaction related to specific aspects of the study (e.g., content of text messages, receiving and responding to text messages, follow-up phone calls from health coach and diabetes educator) at the conclusion of their 6-month participation in the study. After verbal consent is obtained, study staff interview the patient using a survey script that will take approximately 20-25 minutes to complete by telephone.

Study participants will be offered gift cards as an incentive for completing all follow-up assessments. Participants will receive a \$30 gift card for completing the surveys and labs after 90 days and \$40 gift card for completing the surveys and labs after 180 days. The total incentive for each participant who complete all follow-up assessments (at 90 and 180 days) is \$70. In addition, participants will be offered a \$30 gift card for participating in the telephone-based process evaluation survey.

## Statistical Analysis Plan

The statistical software G\*Power was used to estimate the sample size needed to detect differences between groups (DD-CA vs. Usual Care) for the primary outcome, rate of readmission within 30 days post discharge in the proposed randomized-controlled trial. From a pilot study in a similar population, we determined that an absolute reduction of 20% of patients readmitted within 30 days between the two groups would be clinically meaningful based on an estimated 40% readmissions rate within 30-days in the UC arm. Participants will be 1:1 randomized between the study arms, and group assignments will be determined by a random number generator and provided in sealed envelopes to prevent selection bias. Additional assumptions include one-sided alpha = 0.05, and power = 0.80. We estimate maximum of 15% of participants being excluded from analyses due to loss to follow up or request to withdraw. Given these assumptions,  $N = 172$  participants are needed to detect a difference in readmission rates of this magnitude between study arms by a Fisher's Exact test.

The statistical software R and SPSS will be used for all analyses. Patient-reported indicators and clinical will be compared between groups to assess randomization among study arms by Chi-squared tests of proportions to compare categorical variables and student's  $t$ -tests to compare continuous variables. For our first aim we will compare rates of readmissions between the DD-CA and Usual Care groups within 30 days of discharge following study enrollment. The electronic medical records will be used to identify admissions for any patients in the study during each patient's unique follow up period. Unadjusted between-group differences will be analyzed by comparing proportion of patients with any hospital readmissions within the 30-day period by a Fisher's exact test.. For our second aim we will compare glycemic control between groups through HbA1c measurements captured for each study participant 90-days post discharge. Unadjusted group mean differences in HbA1c at each of the two timepoints will be assessed with a student's  $t$ -test.

Our secondary outcomes will be measured through self-report assessments. Baseline patient-reported outcome surveys will be administered immediately after enrollment and prior to randomization. At 90-days, research assistants will obtain the patient-reported outcomes assessment during the follow-up visits and changes from baseline will be compared between groups by  $t$ -tests at each time point. An additional secondary outcome will compare rates between groups of new COVID-19 infections over the 90-day follow-up window via the COVID-19 Patient Survey. Differences in proportions of patients experiencing new infections per group will be compared by Fisher's exact tests. Similar to our primary outcome, we will also examine differences in 90-day hospital readmissions between groups. Unadjusted between-group differences will first be analyzed by comparing proportion of patients with any hospital readmissions within the 90-day period by a Fisher's exact test.

Process outcomes to be assessed following the RE-AIM evaluation framework, and quantitative outcomes will be assessed as follows: To examine enrollment rate, EMR-derived demographic and characteristics of eligible patients will be compared between those who enroll versus decline; where continuous measures will be compared between groups by student's  $t$ -tests and categorical measures will be compared between groups by Chi-Square tests. To examine generalizability of our sample, distribution of demographics in our sample will be compared to expected distributions of our target population through Chi-square tests. Results of semi-structured interviews will be descriptively analyzed to reveal perceptions of implementation efficacy, challenges, satisfaction, and benefits. Physicians' pre- and post-study perceptions and knowledge of, and identified barriers to successful implementation of a

transitions texting program-DD-CA will also be descriptively analyzed. To quantify successful start-up and continuation of the texting program post-discharge after initial hospital training prior to discharge, text messaging rates will be tracked longitudinally within the DD-CA arm. Participants' satisfaction with the texting program (modified and abbreviated for the current study) will be descriptively compared between groups. Participants' impressions of the program, satisfaction, and challenges/barriers experienced via post-discharge will be further qualitatively analyzed following telephone interviews ( $n = 5-7$ ). Stakeholder and CAB member's feedback will be descriptively analyzed and quantified where appropriate.

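### Aim 2 compares 90-day HbA1c by an unadjusted t-test although every participant has an HbA1c from before allocation; an ANCOVA would be more precise at no cost in data, and the second timepoint needs naming

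*Combined protocol and SAP*

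**What the plan says.** The Statistical Analysis Plan defines the second aim as a comparison of glycaemic control through "HbA1c measurements captured for each study participant 90-days post discharge". The next sentence gives the only HbA1c analysis in the document: "Unadjusted group mean differences in HbA1c at each of the two timepoints will be assessed with a" Student's t-test. No adjusted HbA1c model appears anywhere.

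Other places bear on this:

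- **Inclusion criteria (DD-CA Protocol).** One criterion begins "Have type 2 diabetes diagnosis and A1c" and sets a threshold of at least 7%, measured in the last 30 days. Eligibility, consent and the baseline survey all come before the group assignment is revealed.
- **Patient-reported outcomes (SAP).** Here baseline is used: "changes from baseline will be compared between groups by" t-tests.
- **Baseline balance check (SAP).** Patient-reported and clinical measures "will be compared between groups to assess randomization among study arms".
- **Incentives (DD-CA Protocol).** Participants receive a "gift card for completing the surveys and labs after 180 days", and a similar one after 90 days. HbA1c is not named as one of the labs.
- **Sample size (SAP).** The only alpha is the one given for readmission: "Additional assumptions include one-sided alpha = 0.05, and power = 0.80". No SD, effect size or power is given for HbA1c.

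**The concern.** A patient's HbA1c at entry would ordinarily be expected to predict the value 90 days later. When such a measurement exists for everyone before allocation, an analysis that ignores it leaves explainable between-patient variation in the error term. The confidence interval for aim 2 is then wider, and the power lower, than the same patients could give. The trial was sized for readmission, so using the available data better is the one way to sharpen aim 2 without more patients. The plan gives no reason for using baseline with the patient-reported outcomes but not with HbA1c.

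The timepoint wording is a separate, smaller matter. One time is named and two are tested. If the second is baseline, the test repeats the balance check. If it is 180 days, there are two HbA1c tests and no statement of how the second ranks against the first.

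**Working it through.** **The plan's own figure.** Exact power of a one-sided Fisher test at alpha 0.05, 40% against 20%, first reaches 80% at 73 per arm (power 0.803). Then 2 × 73 = 146 and 146 / 0.85 = 171.8, rounded up to 172. The stated N reproduces. It was set for readmission and says nothing for or against the HbA1c analysis.

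**Inputs for HbA1c.**

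- Analysed patients: 172 × 0.85 = 146.2, so 73 per arm. The 15% comes from the sample-size paragraph ("We estimate maximum of 15% of participants being excluded from analyses").
- Correlation ρ between eligibility and 90-day HbA1c: not in the documents; assumed 0.3 to 0.7.
- Alpha: none is stated for HbA1c, so two-sided 0.05 and one-sided 0.05 are both shown.

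**Variance.** The ANCOVA variance relative to the unadjusted t-test is 1 − ρ². At ρ = 0.5 this is 0.75, equivalent to 1 / 0.75 = 1.33 times as many patients. The price is one degree of freedom, a variance factor of about 1 + 1/(146 − 4) = 1.007, not included below.

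**Detectable difference and power.** With n per arm, the noncentrality is δ√(n/2) / √(1 − ρ²), with δ in SD units, referred to the noncentral t with 2n − 2 degrees of freedom (t-test, ρ set to 0) or 2n − 3 (ANCOVA). Solving for 80% power at n = 73, the t-test detects 0.467 SD (two-sided) or 0.414 SD (one-sided). For ANCOVA:

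| ρ | 1 − ρ² | Detectable, two-sided (SD) | Power at 0.467 SD | Detectable, one-sided (SD) | Power at 0.414 SD |
|---|---|---|---|---|---|
| 0.3 | 0.91 | 0.445 | 83.6% | 0.395 | 83.2% |
| 0.4 | 0.84 | 0.428 | 86.4% | 0.379 | 85.7% |
| 0.5 | 0.75 | 0.404 | 89.9% | 0.358 | 89.0% |
| 0.6 | 0.64 | 0.374 | 93.8% | 0.331 | 92.8% |
| 0.7 | 0.51 | 0.333 | 97.5% | 0.295 | 96.7% |

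Below that range the two-sided figures are 0.457 SD and 82% at ρ = 0.2, and 0.465 SD and 80.4% at ρ = 0.1.

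**Fewer HbA1c results.** If only 60 per arm have a 90-day value, the two-sided detectable difference is 0.516 SD unadjusted, against 0.492, 0.447 and 0.368 SD at ρ = 0.3, 0.5 and 0.7.

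**Change score as an alternative.** With equal SDs its variance relative to the t-test is 2(1 − ρ): 1.40, 1.00 and 0.60 at ρ = 0.3, 0.5 and 0.7. ANCOVA gives 0.91, 0.75 and 0.51. Copying the method used for the patient-reported outcomes would therefore not be an equal substitute, and at low ρ would be worse than the planned test.

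**If the second timepoint is 180 days.** Two unranked tests, each at 0.05, give a chance of at least one false positive of 1 − 0.95² = 9.75% if independent. Under a bivariate normal with test correlation 0.5 it is 9.1% (two-sided) or 8.8% (one-sided); with 0.8 it is 7.8% or 7.5%. These figures do not apply if the second timepoint is baseline.

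**The case against.** The strongest reply is that this is a matter of efficiency, not an error. The t-test is a legitimate analysis of a randomised comparison, aim 2 is not the primary outcome, and without an HbA1c target the documents cannot show that 0.47 SD is inadequate. That stands, and no bias is alleged.

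The gain also rests on an assumed correlation. Restricting entry to 7% and above, with a value up to 30 days old, may lower it; at 0.1 the benefit is almost nil. That stands too. It shrinks the gain without turning it into a material loss, since the price is one degree of freedom.

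The word unadjusted, and the SAP's statement that 90-day readmissions will first be analysed without adjustment, may hint at adjusted analyses to follow. But no HbA1c model is written down, and one chosen after the data are seen would not be pre-specified.

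On timepoints, aim 2 is defined at 90 days, which points to the deciding time, and the SAP names no 180-day HbA1c analysis. Baseline and 90 days is at least as natural a reading. The multiplicity figure is therefore conditional and secondary; the wording still leaves the second time open.

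Finally, validity of either analysis assumes that missing 90-day values do not distort the comparison. The plan gives no missing-data method for HbA1c, and ANCOVA does not by itself settle that.

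**Conclusion.** The concern holds. A pre-allocation HbA1c is required of every participant, and the only planned HbA1c analysis does not use it. The planned test is unbiased under randomisation, given complete data or ignorable missingness, but less precise than ANCOVA. For correlations of 0.3 to 0.7 and 73 per arm, power for a difference that the t-test detects with 80% would rise to about 84% to 98% (two-sided) or 83% to 97% (one-sided). The lower end deserves more weight because of the eligibility threshold. The correlation and the HbA1c alpha are assumptions; the existence of the covariate is not. The undefined second timepoint is a clarification to make at the same time. This change should be made, but the trial's validity does not depend on it.

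**What to change.** Rewrite the aim 2 sentences of the SAP so that:

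- the main analysis is an ANCOVA of 90-day HbA1c on arm and eligibility HbA1c, taking the most recent value before randomisation if there are several;
- the result is the adjusted mean difference with a 95% confidence interval, with alpha and sidedness stated;
- the unadjusted t-test stays as a sensitivity analysis;
- the timepoints are named. If the second is baseline, move it to the balance-check sentence. If it is 180 days, state that the 90-day test decides aim 2 and treat 180 days as supportive, in a separate ANCOVA or a repeated-measures model.

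The cost is SAP wording and one degree of freedom. The covariate is already collected for eligibility, so no new data or patients are needed.

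### Does the Aim 2 HbA1c comparison need a stated level, sidedness and deciding timepoint before it can be trusted?

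*Combined protocol and SAP*

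**What the plan says.** The sample size paragraph of the Statistical Analysis Plan concerns "for the primary outcome, rate of readmission within 30 days post discharge in the proposed randomized-controlled trial". Its inputs include the only significance level in the documents: "Additional assumptions include one-sided alpha = 0.05, and power = 0.80".

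Aim 2 is set out in two sentences. The first defines it: "For our second aim we will compare glycemic control between groups through HbA1c measurements captured for each study participant 90-days post discharge". The second gives the test: "Unadjusted group mean differences in HbA1c at each of the two timepoints will be assessed" with a Student's t-test. It states no level or sidedness and does not identify the two timepoints.

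The secondary comparisons are equally brief. For patient-reported outcomes, "changes from baseline will be compared between groups by" t-tests. For COVID-19, "Differences in proportions of patients experiencing new infections per group will be compared by" Fisher's exact tests. For later readmission, "Similar to our primary outcome, we will also examine differences in 90-day hospital readmissions between groups", again by Fisher's exact test. None carries a level or a direction, and there is no general significance statement.

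The DD-CA Protocol section schedules assessments at baseline, 90 days and 180 days. Its incentive paragraph mentions a "gift card for completing the surveys and labs after 180 days", so some laboratory work is expected at 180 days. HbA1c itself is listed among the items taken from the health record audit.

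**The concern.** Two readings of the level are possible. An analyst could carry over the plan's only level, one-sided 0.05, or use the conventional two-sided 0.05. Both would be following the text, and on the same HbA1c data one could report a significant benefit and the other not.

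The timepoint adds to this. The aim sentence has one timepoint and the test sentence has two. If the two are 90 and 180 days, and if a significant result at either were taken as success, the chance of a false benefit claim would rise further. At the extreme it would be nearly four times the strictest reading. Aim 2 is one of only two numbered aims, so a reader might expect its decision rule to be fixed before outcome data are seen.

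**Working it through.** **1. The plan's own figure.** Inputs from the sample size paragraph: readmission 40% versus 20%, one-sided alpha 0.05, power 0.80, 15% loss, Fisher's exact test, 1:1 allocation. By exact enumeration, power is 0.797 with 72 per arm and 0.803 with 73 per arm, so 73 per arm is needed. Then 2 × 73 = 146, and 146 / 0.85 = 171.8, which rounds up to 172. The stated N reproduces. With a two-sided 0.05 Fisher test, 73 per arm would give power of only 0.705, so the one-sided level is clearly the one behind the primary sizing.

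**2. Aim 2 at 90 days, sidedness only.** With no true effect, the chance of a significant result in the benefit direction is 5.0% at one-sided 0.05 and 2.5% at two-sided 0.05.

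**3. How often the two conventions disagree about benefit.** With n per arm, the smallest significant difference in SD units is t × √(2/n), with 2n − 2 degrees of freedom.

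- 73 per arm (172 less 15%): √(2/73) = 0.1655. One-sided: 1.6555 × 0.1655 = 0.274 SD. Two-sided: 1.9766 × 0.1655 = 0.327 SD.
- 86 per arm (no loss): 0.252 SD and 0.301 SD.

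Only an observed benefit between the two thresholds is judged differently. The documents give no HbA1c SD or target difference, so the true difference is an assumption, shown over a range (noncentral t, 73 per arm):

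| True difference (SD) | Significant, one-sided 0.05 | Significant benefit, two-sided 0.05 | Disagree |
|---|---|---|---|
| 0 | 5.0% | 2.5% | 2.5% |
| 0.1 | 14.8% | 8.7% | 6.1% |
| 0.2 | 32.9% | 22.4% | 10.5% |
| 0.3 | 56.3% | 43.7% | 12.7% |
| 0.4 | 77.6% | 67.0% | 10.6% |
| 0.6 | 97.5% | 95.0% | 2.6% |

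Disagreement peaks near 0.3 SD, at about one trial in eight, and is small at both ends.

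**4. The 90-day readmission test.** Assuming rates of 50% and 35%, which are not in the documents, Fisher power at 73 per arm is 53.2% one-sided and 39.8% two-sided, a gap of 13.4 points. At 86 per arm it is 58.8% and 46.4%, a gap of 12.4 points after rounding from 0.5879 and 0.4644.

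**5. If a win at either of two post-discharge timepoints counted.** Treating the two HbA1c tests as bivariate normal, with an assumed correlation r between them and no true effect:

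| r | Each one-sided 0.05 | Each two-sided 0.05, benefit direction |
|---|---|---|
| 0.3 | 9.3% | 4.8% |
| 0.5 | 8.8% | 4.5% |
| 0.8 | 7.5% | 3.9% |

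Against 2.5%, the one-sided column is a ratio of 3.0 (7.5 / 2.5, r = 0.8) to 3.7 (9.3 / 2.5, r = 0.3). This needs four things at once: the pair is 90 and 180 days, the one-sided level carries over, either timepoint suffices, and the correlation is low. The third is stated nowhere.

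**6. Which two timepoints.** The Statistical Analysis Plan never mentions 180 days; its named follow-up windows are 30 and 90 days. Its patient-reported paragraph describes a baseline survey and a 90-day survey, then also refers to testing at each timepoint. Within that section, baseline and 90 days fits well, and every participant has a recent HbA1c at entry because eligibility requires one. In that case there is only one post-discharge test and step 5 does not arise. Against this, a baseline HbA1c comparison would partly duplicate the check on randomisation, and the protocol's 180-day labs make 90 and 180 days a fair reading too. Either way, the aim sentence names 90 days.

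**The case for a change.** The strongest case for a change is that neither default can be read off the page. Two-sided 0.05 is the usual convention, but the only level this plan states is one-sided. The one-sided level is given only as a sizing input for a different outcome. Saying that 90-day readmission is handled similarly to the primary outcome hints at a carry-over without stating it. At modest true effects the choice can change the word significant in about one trial in eight to ten. The remedy would be two or three sentences, with no effect on N, data collection or conduct.

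Most of that stands as a description. The absences are confirmed and the figures are correct. What does not stand is the step from silence to defect. Aim 2 has no power target and no declared success criterion, so there is no formal pass or fail for the ambiguity to corrupt. Saying that nothing points to a deciding timepoint goes too far, because the aim sentence names 90 days. The near-fourfold figure depends on an either-timepoint rule inferred from silence. Choosing two-sided over one-sided is a preference, not a better method, and it has a cost: at an assumed true difference of 0.4 SD, power would fall from 77.6% to 67.0%.

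**Conclusion.** No change is called for. The plan leaves out the level and sidedness for Aim 2 and the secondary tests, and it does not name the two HbA1c timepoints. No stated rule gives a wrong result. The t-tests and Fisher tests are sound under either convention, and a report that gives the 90-day difference with a confidence interval, the p-value and its sidedness lets any reader apply either threshold. An analyst can fill the gap sensibly by taking 90-day HbA1c as the answer to Aim 2, treating any other timepoint as supporting, and saying which convention was used.

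The size of what is left open is a false-benefit rate of 2.5% or 5.0% for 90-day HbA1c. The two conventions disagree in about 2.5% to 13% of trials with 73 per arm. This rests on assumed true differences of 0 to 0.6 SD and on the planned 15% loss. The 30-day readmission test, N = 172 and its 80% power do not depend on any of this.

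### Patient-reported scales are to be compared by t-tests on change from baseline; ANCOVA on the baseline already collected is at least as precise in large samples and costs almost nothing.

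*Combined protocol and SAP*

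**What the plan says.** The secondary-outcome part of the Statistical Analysis Plan has the patient-reported outcomes obtained at 90 days and states that "changes from baseline will be compared between groups by" t-tests at each time point. No baseline-adjusted model is given for these scales anywhere in the plan. The DD-CA Protocol section lists the instruments, among them "Diabetes distress, measured using the Diabetes Distress Scale", the diabetes self-care activities survey and PROMIS Global-10. It schedules the assessments "at baseline/prior to hospital discharge, and at 90 days and 180 days by telephone".

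On timing, the SAP says: "Baseline patient-reported outcome surveys will be administered immediately after enrollment and prior to randomization". The protocol section agrees that the survey comes before the patient's assignment is known: "research staff verbally administer the baseline survey, then unveil the group assignment".

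**The concern.** A t-test on change subtracts the whole baseline score, so it assumes that each extra point at baseline carries one extra point at follow-up. If the true slope is below 1, this over-corrects and adds noise. With equal SDs at the two times and a correlation below 0.5, the change score is less precise than ignoring baseline altogether. ANCOVA estimates the slope from the data.

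N = 172 was set for 30-day readmission. The patient-reported scales have no sample size of their own, so their precision is whatever that number gives. Here the baseline is taken in hospital and the follow-up by telephone about 90 days later, so a slope of exactly 1 should not be taken for granted.

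**Working it through.** **The plan's own figure.** The inputs are 40% versus 20% readmitted, Fisher's exact test, 1:1 allocation, and "Additional assumptions include one-sided alpha = 0.05, and power = 0.80". The smallest size with exact power of at least 0.80 is 73 per arm (power 0.803), or 146 in total. For losses the SAP says: "We estimate maximum of 15% of participants being excluded from analyses due to loss to follow up or request to withdraw". Then 146 / 0.85 = 171.8, rounded up to 172, so the stated N reproduces. I use 73 per arm below as an illustration; the plan does not state an expected loss at 90 days for these scales.

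**Large-sample variances.** Let rho be the baseline-to-follow-up correlation and k the follow-up SD divided by the baseline SD. In units of baseline variance, and apart from a common factor:

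- change score: 1 + k² − 2·rho·k
- ANCOVA: k²(1 − rho²)
- difference: 1 − 2·rho·k + rho²k² = (1 − rho·k)², which is never negative and is zero only when the slope rho·k equals 1

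With k = 1 the ratio of ANCOVA to change-score variance is (1 − rho²) / [2(1 − rho)] = (1 + rho)/2. The change score's 2(1 − rho) exceeds the follow-up-only variance of 1 when rho < 0.5.

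**Ratios.** The documents give neither rho nor k, so both are assumed.

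| k | rho 0.3 | rho 0.5 | rho 0.8 |
|---|---|---|---|
| 0.8 | 0.502 | 0.571 | 0.640 |
| 1 | 0.650 | 0.750 | 0.900 |
| 1.25 | 0.784 | 0.893 | 1.000 |

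The two extremes, worked through:

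- k = 0.8, rho = 0.3: 0.64 × 0.91 / (1 + 0.64 − 0.48) = 0.5824 / 1.16 = 0.502
- k = 1.25, rho = 0.8 (slope 1): 1.5625 × 0.36 / (1 + 1.5625 − 2) = 0.5625 / 0.5625 = 1.000

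**Cost of estimating the slope.** With a normally distributed baseline, ANCOVA variance is multiplied by 1 + 1/(N − 4). This is 1 + 1/142 = 1.0070 at N = 146 and 1 + 1/168 = 1.0060 at N = 172. The factor reflects chance baseline imbalance between arms. The lost error degree of freedom (144 to 143) only moves the two-sided critical value from 1.9766 to 1.9767.

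With the factor included at 73 per arm, the k = 1 ratios are 0.655, 0.755 and 0.906, and the worst case in the table (slope 1) is 1.007. Break-even at k = 1 is rho = 2/1.0070 − 1 = 0.986. Simulation with 200,000 trials per case at 73 per arm gave 0.653, 0.754 and 0.906 for k = 1, and 1.007 for the slope-1 case.

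**Detectable difference.** The calculation uses the noncentral t distribution, 80% power, k = 1 and 73 per arm, with the slope cost included. The standard error is √(2V/73), where V is 2(1 − rho) for the change score and (1 − rho²) × 1.0070 for ANCOVA. Results are in follow-up SDs, change score then ANCOVA.

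| rho | one-sided 0.05 | two-sided 0.05 | relative fall |
|---|---|---|---|
| 0.3 | 0.489 → 0.396 | 0.552 → 0.447 | 19% |
| 0.5 | 0.414 → 0.359 | 0.467 → 0.406 | 13% |
| 0.8 | 0.262 → 0.249 | 0.295 → 0.281 | 5% |

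The SAP states its one-sided alpha for the primary outcome only and gives none for the scales, so both versions are shown. The relative fall is the same either way.

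**The case against.** The planned test is unbiased under randomisation. The outcomes are secondary and carry no power target, so nothing the plan claims is false. Every figure for the gain rests on an assumed correlation and SD ratio, and the range includes zero gain and a 0.7% loss. At a correlation of 0.8 with equal SDs, the detectable difference improves by only about 5%. On this view the change is optional.

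Most of that stands as a description. The documents support the direction of the gain but not its size, and the point is one of efficiency. It does not remove the case for acting, because the trade is lopsided: over the assumed range the variance falls by up to about half, and the worst loss is 0.7%. Both methods need the same two scores per patient, so the switch excludes no one.

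There is also a fair point about scope. The argument covers continuous scores. It does not cover the new COVID-19 infection outcome, which is binary and keeps Fisher's exact test. The COVID-19 knowledge and attitude items have no stated scoring.

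**Conclusion.** The concern holds as a low-cost gain in precision on secondary outcomes; the plan as written is not in error. In large samples ANCOVA is at least as precise as the planned analysis for any correlation and SD ratio. With 1:1 allocation this remains true if the slopes differ between arms. At 73 per arm and equal SDs, ANCOVA is more precise for any correlation below about 0.986. The actual gain is unknown until the sponsor has a correlation and SDs for these scales. Readmission, its Fisher test and the sample size are untouched.

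**What to change.** In the secondary-outcome paragraph of the SAP, replace the change-score t-test with ANCOVA for each continuous patient-reported scale: the 90-day score as outcome, with study arm and the baseline score of the same scale as covariates. Report the adjusted mean difference with its confidence interval. Name the scales covered: the Diabetes Distress Scale, the self-care activities survey, PROMIS Global-10, and any COVID-19 survey score the sponsor will treat as continuous. Apply the same model at any other follow-up time to be analysed. If a mixed model is preferred, include a baseline-by-time term so that the slope can differ by visit; the figures above cover ANCOVA at a single time.

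The cost is about one sentence of SAP text, one degree of freedom per scale, and slightly more analysis work in software the plan already names ("The statistical software R and SPSS will be used for all analyses"). No new data, visits or patients are needed.
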